1.1 Study Objectives

1.1.1 Primary Objective

The primary objective of the study is to:

Determine the efficacy of lemborexant 5 mg (LEM5) and 10 mg (LEM10) compared to placebo (PBO) on subjective sleep onset latency (sSOL) after 6 months of treatment in subjects with insomnia disorder

1.1.2 Secondary Objectives

Key Secondary Objectives

- Determine the efficacy of LEM5 and LEM10 compared to PBO on subjective sleep efficiency (sSE) after 6 months of treatment in subjects with insomnia disorder
- Determine the efficacy of LEM5 and LEM10 compared to PBO on subjective wake after sleep onset (sWASO) after 6 months of treatment in subjects with insomnia disorder

Additional Secondary Objectives

- Determine the efficacy of LEM5 and LEM10 compared to PBO on sSOL, sSE, sWASO, and subjective total sleep time (sTST):
 - over the 1st 7 nights of treatment
 - after 1 month of treatment
 - after 3 months of treatment
- Determine the efficacy of LEM5 and LEM10 compared to PBO on sTST at 6 months

- Evaluate the proportions of sleep onset and sleep maintenance responders to LEM5 and LEM10 compared to PBO as defined by response on sSOL or sWASO at 6 months and 12 months
- Evaluate the safety and tolerability of LEM5 and LEM10
- Evaluate the efficacy of LEM5 and LEM10 compared to PBO as measured by responses on the Insomnia Severity Index (ISI) and the Fatigue Severity Scale (FSS) after 6 months
- Evaluate rebound insomnia following discontinuation of treatment
- Evaluate morning sleepiness during and following completion of treatment
- Evaluate persistence of efficacy of LEM5 and LEM10 over 12 months

1.1.3 Exploratory Objectives

The following will be explored for both LEM5 and LEM10 compared to PBO over Period 1 and over Period 2 with analyses dependent on whether subjects received active treatment or PBO during Period 1:

- Efficacy on quality of sleep
- Health outcomes on the EuroQOL version 5D-3L (EQ-5D-3L), Work Productivity and Activity Impairment Questionnaire – General Health (WPAI-GH), and Patient Global Impression – Insomnia (PGI-Insomnia)
- Efficacy on sSOL, sSE, sWASO, sTST, ISI, and FSS
- Withdrawal symptoms after completion of treatment (Period 2 only)

The following will be explored for LEM5 and LEM10:

- Plasma concentrations of lemborexant and its metabolites M4, M9, and M10
- Population pharmacokinetic (PK) modeling for lemborexant
- PK/pharmacodynamic (PD) relationships between lemborexant concentrations and efficacy and safety variables

1.2 Overall Study Design and Plan

This study was a 12-month, multicenter, randomized, controlled, double-blind, parallel-group study of 2 doses of lemborexant in approximately 900 male and female subjects with insomnia disorder (subjects who complain of difficulties with sleep onset and/or sleep maintenance). Approximately 40% of the population was planned to be 65 years of age or older.

The study had 2 phases, the Prerandomization Phase and the Randomization Phase. The Prerandomization Phase comprised 3 periods and lasted up to 35 days: a Screening Period, a Run-In Period, and a Baseline Period. The Randomization Phase comprised a 6-month, placebo-controlled treatment period (Period 1) followed by a further 6 months in which

subjects received only active treatment (Period 2). Subjects were informed that they were to receive PBO at some point during the study and that all would receive active drug for at least 6 months. They were not informed of either the timing of these periods or the timing of the 2nd randomization. A 2-week Follow-Up Period was then to take place, followed by an End of Study Visit. The study design is shown in Figure 1.

[figure not shown]

Figure 1 Schematic Diagram of Study Design

R = randomization

2 DETERMINATION OF SAMPLE SIZE

The sample size was estimated for the comparison of LEM10 and LEM5 with PBO, with respect to the mean change from Study Baseline at the end of Month 6 of the mean sSOL, the mean sSE and mean sWASO. This estimate was based on a sequential gate-keeping procedure at the 0.05 α -level in Section 3.3.3. There was sufficient power for both the primary endpoint (sSOL) and key secondary endpoints (sSE and sWASO).

On the basis of the dose-finding study E2006-G000-201 (Study 201), across various lemborexant doses (1 to 25 mg) at Days 8 to 15, the standard deviation of change from Study Baseline for sSOL was assumed to be 33 minutes; for sSE was assumed to be 12%; and for sWASO was assumed to be 43 minutes. The LS mean treatment differences at Days 8 to 15 from Study 201 were as follows: for sSE 9.5% for LEM10 and 5.5%, for LEM5; for sWASO -26.6 minutes for LEM10, and -11.3 minutes for LEM5. As a result of the non-normal distribution of sSOL, the LS mean treatment difference is not available (geometric mean ratios were used). Therefore, estimating treatment difference using medians at Days 8 to 15 from Study 201, leads to a median treatment difference of approximately -6.8 minutes for LEM10. For LEM5, a median treatment difference was approximately -13.2 minutes.

To detect a treatment difference in sSOL of at least -8.7 minutes, a sample size of 300 per treatment group at 5% (2-sided) level of significance had >90% power for comparing a dose of lemborexant with PBO.

To detect a treatment difference in sSE of at least 5.5%, a sample size of 300 per treatment group at 5% (2-sided) level of significance had >99% power for comparing a dose of lemborexant with PBO.

For sWASO, a total of 900 subjects (300 per treatment group) gave 90% power to detect a difference of -11.4 minutes for LEM5 and LEM10 compared to PBO (Table 2). The study was adequately powered to show the statistically significant difference from PBO for LEM10 as well as for LEM5.

Table 2 Sample Size Calculations for Study E2006-G000-303

Alpha=0.05	Difference between Active and Placebo CfB (min)	Power = 80%		Power = 90%	
		Sample size per group	Overall 3 group sample size	Sample size per group	Overall 3 group sample size
sSOL (SD=33)	-6.8	371	1113	496	1488
	-7.6	300	900	398	1194
	-8	269	807	359	1077
	-8.7	229	687	300	900
	-9	213	639	284	852
	-10	172	516	230	690
	-11	143	429	191	573
sWASO (SD=43)	-9	360	1080	481	1443
	-9.9	300	900	398	1194
	-10	292	876	390	1170
	-11	241	723	323	969
	-11.4	225	675	300	900
	-12	203	609	271	813

CfB = change from baseline, sSOL = subjective sleep onset latency, sWASO = subjective wake after sleep onset.

The study also had adequate power for the secondary analysis of responders. A sleep onset responder was defined as follows: sSOL at Study Baseline was ≥ 30 minutes and mean sSOL at 6 months was ≤ 20 minutes, and a sleep maintenance responder was defined as follows: sWASO at Study Baseline was ≥ 60 minutes and mean sWASO at 6 months was ≤ 60 minutes and showed a reduction of > 10 minutes compared to Study Baseline. A total of 900 subjects gave >99% power to detect a treatment difference in sleep onset responder rates of 16% and sleep maintenance responder rates of 24.4%, both compared with placebo.

The above sample size also met regulatory safety requirements. Even with early discontinuation rates as high as 50% at Month 6 (ie, 150 subjects remaining) and 60% by Month 12 (ie, 120 subjects remaining in each treatment group), the requirement for 100 subjects in each of the elderly and non-elderly age-groups to complete 12-months of treatment on 5 or 10 mg lemborexant would be met. In addition, a total of 420 subjects would complete 6 months of treatment with 5 or 10 mg lemborexant.

3 STATISTICAL METHODS

All statistical analyses will be performed by the sponsor or designee. When all subjects have completed Treatment Period 1 (Period 1), all data will be unblinded to the sponsor. There will be 3 database locks. The first will be of Period 1 data only, where data up to and including the visit at Month 6 will be analyzed. The second will include all data (Period 1 and ongoing Period 2 data) after all continuing subjects have completed the Month 9 (Period 2) visit, all available data will be analyzed to support regulatory submissions. The third will include all data where the study has continued to completion.

For the Period 1 analysis, sponsor staff and certain designees (detailed in the Study Integrity Charter) will be unblinded to the treatment allocation; however, subjects, investigators, and site personnel will remain blinded. These are not considered formal interim analyses since the primary and key secondary efficacy endpoints are all at Month 6 (Period 1), and there is no placebo control group in Period 2. Therefore, no Type I error adjustment is needed for efficacy analysis.

All descriptive statistics for continuous variables will be reported using number of observations (n), mean (arithmetic unless otherwise specified), standard deviation (SD), median, minimum and maximum. Categorical variables will be summarized as number and percentage of subjects. In summaries for safety the denominator for all percentages will be the number of subjects in a given treatment group. sSOL will be log transformed in analyses unless otherwise stated.

All statistical tests will be based on the 5% level of significance (two-sided).

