	-11.4	225	675	300	900
	-12	203	609	271	813

CFB = change from baseline, sSOL = subjective sleep onset latency, sWASO = subjective wake after sleep onset.

The study also has adequate power for the secondary analysis of responders. A sleep onset responder is defined as follows: sSOL at Study Baseline is ≥ 30 minutes and mean sSOL at 6 months is ≤ 20 minutes, and a sleep maintenance responder is defined as follows: sWASO at Study Baseline is ≥ 60 minutes and mean sWASO at 6 months is ≤ 60 minutes and shows a reduction of >10 minutes compared to Study Baseline. A total of 900 subjects gives $>99\%$ power to detect a treatment difference in sleep onset responder rates of 16% and sleep maintenance responder rates of 24.4%.

The above sample size also meets regulatory safety requirements. Even with early discontinuation rates as high as 50% at Month 6 (ie, 150 subjects remaining) and 60% by Month 12 (ie, 120 subjects remaining in each treatment group), the requirement for 100 subjects in each of the elderly and non-elderly age-groups to complete 12-months of treatment on 5 or 10 mg lemborexant will be met. In addition, 420 total subjects would have completed 6 months of treatment of 5 mg or 10 mg lemborexant.

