Timepoints where results are available	Wk1	M1	M2	M3	M4	M5	M6																																																											
Pattern 1	x	x	x	x	x	x	x																																																											
Pattern 2	x	x	x	x	x	x	.																																																											
Pattern 3	x	x	x	x	x	.	.																																																											
Pattern 4	x	x	x	x	.	.	.																																																											
Pattern 5	x	x	x																																																											
Pattern 6	x	x																																																											
Pattern 7	x																																																											
Tipping Point	Imputation towards the null hypotheses: A range of shifts starting from the primary analysis (CCMV) will be used in the multiple imputation of missing data assuming MNAR to identify the specific shift and treatment effect that will tip the results from statistically significant to non-significant.	Sensitivity																																																																
Tipping Point	Imputation towards the null hypotheses: A range of shifts will be used in the multiple imputation of missing data assuming MAR to identify the specific shift and treatment effect that will tip the results from statistically significant to non-significant.	Sensitivity																																																																

Unless stated otherwise, missing values will be considered as non-responders in responder analyses and the continuous variables will be analyzed using MMRM assuming MAR. Details can be found in [Section 3.4](#).

All safety analyses will be performed based on the observed data only.

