3.6.1 Treatment Definitions

For visit-based Safety data (ie, laboratory values, vital signs, ECGs, etc) data will be summarized by treatment (LEM5, LEM10) and duration of exposure to treatment (3, 6, 9 and 12 months). Treatment groups are LEM5 and LEM10, and include both (a) LEM Period 1 subjects on the On-Treatment Safety Analysis Set using the change from Study Baseline and (b) LEM Period 2 subjects previously receiving PBO on the On-Treatment Safety Analysis Set using the change from Period 2 Baseline. Summaries of exposure, AEs, TEMAV, clinically abnormal vital sign and ECG values will be summarized for:

- Period 1 data, where treatment groups are PBO, LEM5 and LEM10 in the Safety Analysis Set (ie, subjects who received at least 1 dose of study drug in Treatment Period 1)

- 12-month LEM exposure, where treatment groups are LEM5 and LEM10 in the On-Treatment Safety Analysis Set (ie., subjects who received at least 1 dose of lemborexant), where data will be summarized by exposure to treatment (3, 6, 9 and 12 months)

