3.6.3.2 Subgroup Analysis of TEAE

Subgroup summaries will be presented for the following summary tables. These summaries will be repeated for the Period 1 (Safety Analysis Set) and 12-month LEM exposure (On-Treatment Safety Analysis Set) separately.

- Overview table of TEAEs, including number of subjects with TEAEs, treatment-related TEAEs, severe TEAEs, treatment-emergent serious AEs (TESAEs), deaths, TEAEs leading to study drug withdrawal
- Incidence of TEAEs by SOC and PT
- Incidence of TESAEs by SOC and PT

The following demographic and baseline information will be used in the subgroup summary:

- Age group 1 (<65, 65 to <75, and ≥75 years old)
- Age group 2 (<65 and ≥65 years old)
- Sex (male and female)
- Race (white, black, Asian, and other)
- Region (North America, Europe and New Zealand, Asia)
- BMI (<25, 25 to 30, >30 kg/m²)

Percentages will be based on the total number of subjects in the relevant treatment group. A subject with 2 or more TEAEs with the same PT (or SOC) will be counted only once for that PT (or SOC).

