3.6.4 Laboratory Values

Laboratory results will be summarized using Système International (SI) units, as appropriate. With the exception of urinalysis, all quantitative parameters listed in [protocol Section 9.5.1.5.3 Laboratory Measurements](#), the actual value and the change from Study Baseline will be summarized at each scheduled visit using descriptive statistics by treatment group. The change from Study Baseline/Treatment Period 2 Baseline (as appropriate) will also be repeated for the 12-month LEM exposure (On-Treatment Safety Analysis Set), summarized by treatment group and duration of exposure.

For urinalysis, the actual and the change from baseline of pH and specific gravity will be summarized at each visit by treatment group. Analysis of changes from baseline will be based on the number of subjects with both nonmissing baseline and relevant postbaseline results.

Laboratory test results will be assigned a low, normal, high (LNH) classification according to whether the value was below (L), within (N), or above (H) the laboratory parameter's reference range. Shifts from Study Baseline (LNH) to each scheduled visit will be provided by treatment group for each laboratory parameter based on Safety Analysis Set. The shift tables will also be repeated for the 12-month LEM exposure (On-Treatment Safety Analysis Set), summarized by treatment group and duration of exposure.

The Sponsor's Grading for Laboratory Values ([Appendix 1](#)) presents the Eisai criteria that will be used to identify subjects with treatment-emergent markedly abnormal laboratory values (TEMAV). Except for phosphate, a TEMAV is determined if a postbaseline grade increases from baseline and the postbaseline grade is greater than or equal to a grade of 2. For phosphate, a TEMAV was defined as a postbaseline value with an increase from baseline to a grade of 3 or higher.

The number (percentage) of subjects with TEMAVs will be summarized by treatment group using the Safety Analysis Set. The number (percentage) of subjects with TEMAVs will be produced separately for the Period 1, up to 12-months treatment, up to 6-months treatment and On-Treatment. When displaying the incidence of TEMAVs, each subject will be counted

once in the laboratory parameter high and in the laboratory parameter low categories, as applicable.

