3.6.7 Other Safety Analyses

3.6.7.1 Columbia-Suicide Severity Rating Scale (C-SSRS)

Suicidality is assessed using a self-rated electronic version of the C-SSRS (eC-SSRS). The eC-SSRS assesses an individual's degree of suicidality, including both suicidal ideation and suicidal behavior. The occurrence of suicidal ideation or suicidal behavior at each visit will be summarized by treatment group using frequency count. A subject will be counted once for each of these categories if at least one question is answered positive belonging to the category.

In addition, self-injurious non-suicidal behavior will also be summarized separately for occurrence in a similar fashion to suicidal ideation and behavior.

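### The SAP's single arm-size denominator for safety percentages understates rates in tables for a given time point wherever only part of the arm was assessed

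*SAP*

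**What the plan says.** The general rule is in SAP section 3: "In summaries for safety the denominator for all percentages will be the number of subjects in a given treatment group". It makes no exception for visit, exposure or subgroup. The same paragraph has categorical variables reported as number and percentage.

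Several planned safety tables refer to a single time point:

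- SAP 3.6.6 gives shift tables of ECG interpretation by time point.
- SAP 3.6.7.1: "The occurrence of suicidal ideation or suicidal behavior at each visit will be summarized by treatment group using frequency count".
- SAP 3.6.7.2 reports the number and percentage with a T-BWSQ total of 3 or more. It is measured at End of Study and analysed on the Safety Analysis Set.
- SAP 3.6.4: "Shifts from Study Baseline (LNH) to each scheduled visit will be provided by treatment group for each laboratory parameter".
- SAP 3.6.5 shows clinically notable vital signs by time point.

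For laboratory values and vital signs, SAP 3.6.4 and 3.6.5 also carry a narrower sentence: "Analysis of changes from baseline will be based on the number of subjects with both nonmissing baseline and relevant postbaseline results". SAP 3.6.6 and 3.6.7 have no counterpart.

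Two further places bear on the denominator. For 12-month lemborexant exposure, SAP 3.6.1 says "data will be summarized by exposure to treatment (3, 6, 9 and 12 months". For the TEAE subgroup tables, SAP 3.6.3.2 says "Percentages will be based on the total number of subjects in the relevant treatment group". SAP 3.3.5 adds: "All safety analyses will be performed based on the observed data only".

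**The concern.** Safety data are not imputed. If a by-visit count is divided by the whole arm, a subject with no ECG or eC-SSRS at that visit enters the denominator but can never enter the numerator. The printed percentage can then fall over time simply because fewer subjects are assessed.

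The SAP treats missing efficacy data in a similar way, counting missing as non-response (SAP 3.3.5 and 3.4.2.4), but it says so, and there the choice works against showing benefit. In safety the same arithmetic lowers the apparent risk, and the SAP does not acknowledge it.

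SAP 3.6 plans no hypothesis tests for safety, so the displayed percentages are the safety result. Twelve-month safety is part of the study rationale (Protocol 7.2), and the late time points are where the denominator matters most.

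**Working it through.** **1. The plan's own retention figures.** Inputs: 300 per group, with discontinuation as high as 50% at Month 6 and "60% by Month 12 (ie, 120 subjects remaining in each treatment group" (Protocol 9.7.2; the same figures are in SAP 2).

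- Month 6: 300 × (1 − 0.50) = 150.
- Month 12: 300 × (1 − 0.60) = 120.
- Completing 6 months on lemborexant: 150 + 150 + 120 = 420.

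All three match the documents.

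**2. Formula.** Let r be the rate among assessed subjects, n the number assessed and N the arm size. There are r × n events, so the printed percentage is r × n/N.

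**3. By-visit percentages.** Assume that only retained subjects are assessed. The values of r are also assumed.

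| r | Month 6 (150/300) | Month 12 (120/300) |
|---|---|---|
| 2% | 1.0% | 0.8% |
| 5% | 2.5% | 2.0% |
| 10% | 5.0% | 4.0% |
| 20% | 10.0% | 8.0% |

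With milder assumed loss, r = 10% prints as 9.0% when 90% are assessed, 8.0% when 80% are, and 7.0% when 70% are.

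**4. Comparison between arms.** With the same r in both arms, the printed ratio is the ratio of the assessed fractions. The documents give no dropout by arm, so these are assumed cases:

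- Placebo 20%, lemborexant 40% dropout: 0.60/0.80 = 0.75.
- Placebo 10%, lemborexant 20%: 0.80/0.90 = 0.89.
- Placebo 50%, lemborexant 30%: 0.70/0.50 = 1.40.

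The distortion can go either way.

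**5. Laboratory shifts and notable vital signs.** SAP 3 makes N the arm. The sentence in SAP 3.6.4 and 3.6.5 makes it subjects with both a baseline and a post-baseline value. A shift needs both values, and every notable vital-sign criterion in SAP Table 8 includes a change from baseline, so the narrower sentence can be read to govern. The SAP does not say which applies.

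**6. By-exposure columns, if SAP 3 is applied literally.** Former-placebo subjects receive lemborexant only in the 6-month Period 2, so they cannot reach 9 or 12 months on it. With no dropout, each dose group has 300 + 150 = 450 subjects, of whom 300 can reach 12 months. A 10% rate prints as 10% × 300/450 = 6.7%. At the upper-bound dropout the group is 300 + 75 = 375 with 120 at 12 months, and 10% prints as 3.2%.

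**7. TEAE subgroups, if the denominator in SAP 3.6.3.2 is the whole arm.** About 40% of subjects are planned to be 65 or older (SAP 1.2). A 20% rate in each age group prints as 20% × 0.40 = 8% in the older group and 20% × 0.60 = 12% in the younger.

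**The case against.** The strongest reply is that the general sentence was written for cumulative incidence, and there it is right. TEAEs, serious adverse events, markedly abnormal laboratory values and the ECG categories based on the maximum post-baseline value all properly use the arm. A reader might infer that every safety percentage is understated. The documents do not support that, given these tables and the paired-value sentence in SAP 3.6.4 and 3.6.5.

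Other points also stand in part:

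- **Subgroups.** In SAP 3.6.3.2, the relevant treatment group may mean the treatment group within that subgroup. The 8% and 12% hold only on the other reading.
- **Exposure.** SAP 3.1.2 defines the safety endpoint for subjects exposed for given durations, and SAP 3.6.7.2 refers to a subgroup by duration. On that reading, former-placebo subjects are not in the 12-month group, and the 6.7% and 3.2% fall away.
- **Dropout.** The 50% and 60% are planning upper bounds. Protocol 9.5.5 encourages subjects who stop drug to attend all visits, and those who leave are scheduled for an ET and an EOS visit, so more subjects may be assessed, including on the T-BWSQ.
- **Observed data.** A reader might see a contradiction with the observed-data sentence in SAP 3.3.5. That sentence most directly rules out imputation. It does not set a denominator.
- **Presentation.** Safety is descriptive, counts accompany percentages, and the table shells are a separate document (SAP 9). A percentage among those still assessed also carries survivor bias.

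The last point does not rescue the rule. Printed counts let a careful reader recompute a rate only if the number assessed is shown, and the SAP text should not depend on shells to correct it. Nor does the frequency-count wording for the eC-SSRS remove it from the rule, since SAP 3 reports categorical variables with percentages.

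**Conclusion.** The concern holds for percentages at a given time point. For ECG interpretation shifts by time point, eC-SSRS by visit and T-BWSQ of 3 or more at End of Study, following SAP 3 as written understates the rate by the factor assessed/arm. At the plan's upper-bound dropout that factor is 0.50 at Month 6 and 0.40 at Month 12, provided that only retained subjects are assessed. Actual attendance may make the shortfall smaller.

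For laboratory shifts and notable vital signs, the finding is two competing rules, not a settled wrong denominator. For by-exposure and subgroup tables it is an ambiguity, with large consequences on the literal reading.

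A reader might also infer that the rule makes lemborexant, or whichever arm loses more subjects, look safer. The arithmetic allows a distortion, but without dropout by arm neither its direction nor its size is known.

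This should be fixed. It is not a must-fix: whole-period incidence, the primary and key secondary analyses and the data collected are unaffected.

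**What to change.** In SAP 3, limit the treatment-group denominator to whole-period incidence (TEAEs, serious adverse events, markedly abnormal laboratory values, maximum post-baseline ECG categories). For by-visit, by-exposure and End of Study percentages, use subjects with a non-missing assessment at that time point, requiring both baseline and post-baseline values where a change or shift is involved, and print that n in the table. This also settles which rule governs laboratory shifts and notable vital signs.

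In SAP 3.6.3.2, state that percentages use the number of subjects in that subgroup within the treatment group.

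The cost is a few sentences and an n assessed in the table shells. The downside is that late percentages rest on fewer subjects and describe only those still assessed, which is why the n must be shown.
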